#### Analysis

TEAEs with missing time and occurring on the day of prime immunization will be assigned to all intervals starting with the prime immunization. TEAEs with missing time and occurring on the day of the boost immunization will be assigned to all intervals including the boost immunization. TEAEs with missing date will be assigned to all the respective intervals if it cannot be ruled out, that it belongs to a time interval.

The following TEAE types will be analyzed:

- Any TEAE
- Related TEAE
- Grade >=3 TEAE
- Related grade >=3 TEAE
- TEAEs with dose limiting toxicity (DLT)
- Any treatment emergent serious adverse event (TESAE)
- Related TESAE
- Deaths

#### Overall summary of TEAEs

The number and percentage of subjects reporting at least one TEAE and the number of TEAEs will be summarized for all TEAE types defined above for each defined time interval.

The same analysis will be done for treatment emergent AESIs (TEAESIs) by time intervals.

The same analysis will be done excluding TEAEs which fulfil the following criteria:

- Are based on solicited reporting via subjects' diaries (all preferred terms included in 'BNT162-01\_AEs\_based\_on\_solicited\_reporting\_via\_subjects\_diaries\_v3.0') and
- For prime or boost immunization, respectively, has a start and end date in the time period between dosing and
  - 1) the day of last diary entry (inclusive) or
  - 2) day 7 after dosing (inclusive)

whatever comes first.

TEAEs with missing start or end date will remain included.

For each defined time interval, the number and percentage of subjects reporting at least one TEAE will be summarized by PT nested within SOC for each of the following AE types: Any TEAE, Related TEAE, Grade >=3 TEAE, Related grade >=3 TEAE, Any TESAE, Related TESAE, TEAEs with unresolved, fatal or unknown outcome, and any TEAE but excluding TEAEs which are based on solicited reporting via diaries as defined for the overall summary.

If a SOC / PT is reported more than once for a subject, the subject will only be counted once for this SOC / PT. All TEAE summary tables will be sorted alphabetically by SOC and PT within SOC.

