- The SRC must assess the safety and tolerability data of the first 6 subjects before allowing progression to the next cohort, for each vaccine per cohort/dose level.
- After each assessment, the SRC may request a prolongation of the observation periods to up to Day 7 for later cohorts. Experience in this ongoing trial and in the ongoing BNT162-02 trial, has confirmed the adequacy of the implemented observations periods.
- The SRC may make recommendations on increasing observation periods and additional subject wellbeing calls may be included at the discretion of the SRC.
- To ensure trial subject safety during the trial, their safety will be monitored from Visit 0 (screening) until approximately 6 months after the last immunization.

For the expansion cohorts:

- Due to the extensive experience and exposure already achieved with BNT162b2 at 30 µg in the ongoing global Phase I/II/III trial (from which frequent, rolling safety data submissions to health authorities are being made) the measures implemented for dose ranging cohorts are deemed unnecessary for the expansion cohorts (by 20 JAN 2021, more than 25,000 trial subjects have been dosed at least once with BNT162b2).
- Immunocompromised individuals are considered at increased risk from infection with SARS-CoV-2 and of infections in general. Risk minimization measures already in place for the protection of all subjects in this trial are also considered sufficient to protect this increased risk group, who are generally regarded as ambulatory in nature. Care should however be taken to avoid unnecessary extension of on site time and site visits for these subjects, to minimize their risk of exposure to high risk pathogens.

Vaccine-related enhanced disease has been reported in the literature from non-clinical studies investigating different vaccine formulations tested to prevent various coronavirus-induced diseases. Such effects have not been documented so far for SARS-CoV-2. No data are currently available to exclude that BNT162 may cause enhanced disease in vaccinated subjects.

The risks linked to the pandemic COVID-19 outbreak will be managed by requiring that the trial subjects:

• Avoid contact with persons tested positive for SARS-CoV-2 antibodies or have an increased risk for infection during their participation in the trial.

Clinical Trial Protocol including Amendments Nos. 01 to 09 BNT162-01 Page 46 of 113 Version: 13.0 Date: 12 JAN 2022

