### 8.2.10 SARS-CoV-2 testing

SARS-CoV-2 testing (PCR-based and antibody-based) will be performed at the time points provided in the SoA (Section 1.3).

This includes PCR-based testing for SARS-CoV-2 as an eligibility criterion and blood draws for anti-SARS-CoV-2 antibody testing as baseline reference for immunogenicity analysis.

If required, this reference will allow the discrimination between vaccinated and infected subjects.

The screen for SARS-CoV-2 by PCR-based test using oral swipe sample can be performed by either a central laboratory or a "point of care" device at the trial site.

- If a central laboratory is used: Only the SARS-CoV-2 status will be tested and no further data will be generated.
- If a point of care device is used: The most commonly used devices come with predefined test panels that test for a range of pathogens and not just for SARS-CoV-2. Thus, inevitably and automatically, incidental data for the pathogens other than SARS-CoV-2 will be generated when using such devices. Since this incidental data is not required by this trial, only the results for SARS-CoV-2 will be recorded in the CRF, analyzed, and reported as described in this protocol. If a test result for SARS-CoV-2 or another pathogen must be reported to relevant authorities, this notification will be done by the trial site.

Clinical Trial Protocol including Amendments Nos. 01 to 09 BNT162-01 Page 73 of 113 Version: 13.0 Date: 12 JAN 2022

The anti-SARS-CoV-2 antibody testing will be performed with a commercially available antibody test. In case this commercial antibody test can, discriminate between vaccine-specific and infection-specific antibody responses (based on the antigens used), it will be used to test subjects who may have experienced enhanced respiratory disease or progression of flu-like symptomatology, such as non-resolution of the symptoms after 7 d, symptom kinetics that are inconsistent with a relationship to RNA immunization, as might be expected with a COVID-19 disease (see Section 6.6.3).

In these cases, ad hoc anti-SARS-CoV-2 antibody testing will be performed to test for the development and presence of SARS-CoV-2-specific antibodies, ideally at approximately 14 d and 28 d after the last immunization with the BNT162 candidate vaccine. This data will be used to evaluate the development and progression of an antibody response allowing the diagnosis of a manifest infection.

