## 8.3.8 Adverse events of special interest

Enhanced respiratory disease or flu-like symptomatology not resolved after 7 d or with symptom kinetics that are inconsistent with a relationship to RNA immunization will be considered adverse events of special interest (AESI).

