#### 6.4.3. Adverse Events

#### Definition

For detailed information on adverse events see section 10.3 of the protocol.

Adverse events (AEs) will be coded using the Updated Version MedDRA® 23.0 including specific terms for COVID-19 to get a system organ class (SOC) and preferred term (PT) for each AE.

A treatment emergent adverse event (TEAE) is defined as any AE with an onset after the first immunization (if the AE was absent before the first immunization) or worsened after the first immunization (if the AE was present before the first immunization). AEs with an onset date more than 28 days after the last immunization will be considered as treatment emergent only if assessed as related to IMP by the investigator. AEs that cannot be determined to not be treatment emergent due to missing date or time will be defined as TEAE.

Clarification: To clarify the definition in the protocol, AEs with an onset date at the date of the first immunization will only be considered as treatment emergent if the AE occurred after the first immunization.

The TEAEs will be evaluated for the following time intervals, clarifying and harmonizing the intervals defined in the protocol:

- Prime immunization up to boost immunization or day 28 (inclusive) after initial immunization (whatever comes first)
- Boost immunization up to day 28 (inclusive) after boost immunization
- All TEAEs (regardless of relationship assessment) occurring from

- Prime immunization up to day 28 after boost immunization (inclusive).
- If no boost immunization, up to 28 days (inclusive) after prime immunization
- All TEAEs assessed as related through visit 10.

The intervals starting or ending with an immunization, will start or end with the date and time of the immunization. TEAEs are assigned to the time intervals according to their start date and time. AEs with missing date will be assigned to each of the respective intervals if it cannot be ruled out, that it belongs to the time interval.

Deviating from the protocol, the time intervals including 7 days after each immunization will not be analyzed.

AEs will be evaluated for the following time interval 'After Day 28 after boost or after prime (if no boost)':

All AEs (regardless of relationship assessment) occurring

- After day 28 after boost immunization
- o If no boost immunization, after 28 days after prime immunization

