AEs are assigned to the time interval according to their start date and time. AEs with missing date will be assigned to the interval if it cannot be ruled out, that it belongs to the time interval.

Adverse events of special interest (AESI)

Enhanced respiratory disease or flu-like symptomatology not resolved after 7 days or with symptom kinetics that are inconsistent with a relationship to RNA immunization will considered AESIs. AESIs are marked in the CRF.

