#### AEs

The number and percentage of subjects reporting at least one AE and the number of AEs will be summarized for the above defined time interval 'After Day 28 after boost or after prime (if no boost)' and the following AE types:

- Any AE
- Related AE
- Grade >=3 AE

- Related grade >=3 AE
- AEs with dose limiting toxicity (DLT)
- Any serious adverse event (SAE)
- Related SAE
- Deaths
- Any AEs linked to confirmed COVID-19 cases (defined as AEDECOD = 'COVID-19')

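### The AESI definition has no time limit, but the SAP counts an AESI that starts more than 28 days after the last dose only if it is rated related, and the after-Day-28 table has no AESI row

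*SAP*

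**What the plan says.** Protocol 2.3.1 leaves the risk open: "No data are currently available to exclude that BNT162 may cause enhanced disease in vaccinated subjects". Protocol 8.3.8 defines the AESI as "Enhanced respiratory disease or flu-like symptomatology not resolved after 7 d or with symptom kinetics that are inconsistent with a relationship to RNA immunization". SAP 6.4.3 repeats this definition and adds that AESIs are marked in the CRF. Neither text sets a time limit or requires a confirmed infection.

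The only AESI tabulation is in SAP 6.4.3, Overall summary of TEAEs: "The same analysis will be done for treatment emergent AESIs (TEAESIs) by time intervals". The definition of treatment-emergent in the same section is: "AEs with an onset date more than 28 days after the last immunization will be considered as treatment emergent only if assessed as related" to the vaccine. The listed intervals for treatment-emergent events end at day 28 after the last dose, apart from one for related events that runs through Visit 10.

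A separate SAP table covers AEs starting after day 28 regardless of relationship. Its rows are any AE, related, grade 3 or higher, related grade 3 or higher, dose-limiting toxicity, serious, related serious, deaths, and "Any AEs linked to confirmed COVID-19 cases". AESI is not among them.

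For subjects with suspected enhanced or prolonged illness, protocol 8.2.10 sets the ad hoc antibody tests "ideally at approximately 14 d and 28 d after the last immunization with the BNT162 candidate vaccine".

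**The concern.** Enhanced disease follows an infection, and an infection can occur at any point in follow-up. The count meant to capture it is tied to the last dose through the treatment-emergent rule.

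The rule also sits badly with the definition. One arm of the AESI is a time course that does not fit a reaction to the RNA vaccine. A late event of that type is likely to be rated unrelated, and that rating removes it from the AESI count. A reported AESI total could then be zero, and be read as covering all follow-up, although events flagged as AESIs are in the database.

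**Working it through.** **Inputs (protocol 1.3, Tables 6 to 9).** Prime Day 1; boost Day 22; EoT Visit Day 50 in the prime/boost cohorts; last visit Day 184 (Cohorts 1 to 10, and 14) or Day 730 (Cohorts 11 to 13). Single-dose BNT162c2: dose Day 1, last visit Day 184.

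**The plan's own intervals reproduce.** 50 − 22 = 28 d; 184 − 22 = 162 d; 730 − 22 = 708 d; single dose 184 − 1 = 183 d.

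**Where a late event goes (onset more than 28 d after the last dose).**

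| Event | In the AESI count? | Elsewhere |
|---|---|---|
| Related, up to Visit 10 | Yes | After-Day-28 rows, listing |
| Related, after Visit 10 (Cohorts 11 to 13 only) | No | After-Day-28 rows and listing, if recorded |
| Unrelated, serious or proven COVID-19 | No | Any-AE, grade 3 or higher, serious, death or COVID-19 rows as applicable; listing |
| Unrelated, not serious, no proven infection | No | Any-AE and grade rows and listing, only if the site records it |

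The last row arises from the collection rules. For Cohorts 11 to 14, protocol 8.3.1 limits collection from Visit 7 through Visit 9 to related AEs, SAEs and SARS-CoV-2 infections, and after Visit 9 to SAEs and infections. Footnotes to Tables 6 and 7 limit the follow-up visits of the other cohorts to related AEs and SAEs, with proven COVID-19 reported in any case. AESIs are not named in any of these rules.

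**Share of planned follow-up after the 28-day limit.** Formula: (last day − day of limit) / (last day − Day 1). The limit is Day 22 + 28 = Day 50 for prime/boost and Day 1 + 28 = Day 29 for single dose.

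- Prime/boost Cohorts 1 to 10, and 14: (184 − 50)/(184 − 1) = 134/183 = 73%.
- Single-dose BNT162c2: (184 − 29)/(184 − 1) = 155/183 = 85%.
- Cohorts 11 to 13: (730 − 50)/(730 − 1) = 680/729 = 93%.

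The second antibody date falls on the same limit, so the same shares apply to it. After the first date (14 d, so Day 36 or Day 15) the shares are 148/183 = 81%, 169/183 = 92% and 694/729 = 95%.

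**Sensitivity.** Protocol 7.1.1 allows a one-week boost delay in Cohorts 11 to 14, which moves the limit to Day 29 + 28 = Day 57. With the earliest permitted last visit, the share is (175 − 57)/(175 − 1) = 118/174 = 68% for a Day 184 schedule and (716 − 57)/(716 − 1) = 659/715 = 92% for Day 730. Subjects in Cohorts 11 to 13 leave at a non-trial SARS-CoV-2 vaccination. Leaving on Day 120 gives 70/119 = 59%, and on Day 365 gives 315/364 = 87%. The share falls to half only if follow-up ends at Day 99: (99 − 50)/(99 − 1) = 49/98.

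**The case against.** The strongest reply is that a label is missing, not the case. The protocol's section on documentation of particular situations requires any proven COVID-19 to be reported up to the last follow-up visit, with moderate or severe cases reported as SAEs, and the after-Day-28 table counts AEs regardless of relationship. This stands. A reader might infer that late cases survive only in a listing; the documents do not support that. What is lost is AESI identity: the COVID-19 row cannot show which cases were flagged as enhanced disease.

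Second, related needs only a reasonable possibility (protocol, Assessment of causality), so an investigator who suspects enhancement can rate the event related, and it is then counted through Visit 10. This also stands, but the count then depends on that judgement, which the time-course arm of the definition pushes the other way. Nothing in the documents says that an investigator cannot make the judgement.

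Third, a reader might infer that the serology would be uninterpretable. The protocol's section on SARS-CoV-2 testing provides for a test that separates vaccine from infection antibodies, or a custom assay if the commercial one cannot. Its dates are ideal and approximate, and symptoms reported by a subject can trigger diagnostic measures at any time. So the point is narrower: no text gives a sample time for illness that starts after both dates. Nor does a 28-day sample after the prime necessarily collide with the boost, because the anchor is the last immunization.

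Fourth, the protocol's section on recording and follow-up of AEs asks for any AE to be documented until discharge, which is broader than the section on the collection period and the schedule footnotes. That softens the collection gap, but it shows that the rules disagree.

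Finally, the trial is descriptive, uncontrolled and small, so an extra AESI row would not settle whether enhancement occurs.

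**Conclusion.** The point holds as a gap in tabulation and ascertainment. The AESI definition is not tied to a dose; the treatment-emergent filter and the antibody dates are. Under the plan, an AESI rated unrelated is counted as one for 49/183 d (27%) of follow-up from prime in the Day 184 prime/boost cohorts, 28/183 d (15%) in the single-dose cohorts and 49/729 d (7%) in Cohorts 11 to 13.

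These figures are shares of planned time. A reader might take the complements (73%, 85%, 93%) as the share of enhanced-disease cases missed. That would need an even risk of onset over follow-up, and the documents give no infection rate over time. The Cohort 11 to 13 figure also precedes censoring at non-trial vaccination. That most of follow-up lies after the limit holds unless follow-up ends by about Day 99.

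The change is worth making because it costs little and alters what the reported AESI total means. It does not affect the validity of the other safety tables.

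**What to change.** 1. **SAP 6.4.3.** Add a row for any AESI, regardless of relationship, to the after-Day-28 table, cross-classified by confirmed COVID-19. Give an AESI total from prime to the last visit, subject to the existing exclusion of data after a non-trial vaccination. The CRF flag already exists, so recorded events need no new data. If follow-up has ended, this step still stands alone.
2. **Protocol 8.3.1 and the AE footnotes of the schedules.** For remaining follow-up, list AESIs among the events collected after the EoT Visit, and align these texts with 10.3.1.7.
3. **Protocol 8.2.10.** Reconcile the last-dose anchor of the ad hoc antibody samples with the open-ended definition in 8.3.8, so that sample timing is also defined for symptoms starting after day 28. This concerns ascertainment only, not treatment.

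The cost is one extra table row with its total, a wording change in the protocol, and slightly more AE reporting at follow-up visits that already take place.

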## TEAE by grade

The number and percentage of subjects with TEAEs will be summarized by worst grade by PT nested within SOC by time interval. The same table will be created for TEAE but excluding TEAEs which are based on solicited reporting via diaries as defined for the overall summary. The worst grade will be counted if a TEAE is reported more than once by the same subject for this SOC / PT in one time interval. As described in section 10.3.1.7 of the protocol version 8, the grading changed during the study from a 3-point scale to a 4-point scale. The assessment of AE and/or SAE intensity should be done consistently for all subjects treated with the same treatment and dose.

#### AEs

The number and percentage of subjects reporting at least one AE and the number of AEs will be summarized for the above defined time interval 'After Day 28 after boost or after prime (if no boost)' and the following AE types:

- Any AE
- Related AE
- Grade >=3 AE

- Related grade >=3 AE
- AEs with dose limiting toxicity (DLT)
- Any serious adverse event (SAE)
- Related SAE
- Deaths
- Any AEs linked to confirmed COVID-19 cases (defined as AEDECOD = 'COVID-19')

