## Trial duration

In total, the planned trial duration (i.e., the sum of the screening, treatment, and follow-up phases) for subjects is expected to be approximately 223 d for Cohorts 1 to 10 and 14, and 760 d for Cohorts 11 to 13.

For logistical reasons, investigation of the different vaccines may not be able to start at the same time.

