- f) Clinical laboratory tests: (Chemistry) alkaline phosphatase, creatinine, ferritin, C-reactive protein, albumin, alanine aminotransferase, amylase, aspartate aminotransferase, gamma glutamyl transpeptidase, total bilirubin, blood urea nitrogen, glucose, lipase, sodium, potassium, calcium; (Hematology) hemoglobin, hematocrit, red blood cell count, white blood cell count and differential (neutrophils, lymphocytes, monocytes, eosinophils, basophils), platelet count. Only in women who are not WOCBP (to confirm postmenopausal status): follicle stimulating hormone at Visit 0.
- g) Viral screening for human immunodeficiency virus (HIV) 1 or 2, hepatitis B, hepatitis C.
- h) Flexibility for visit days: Visit 3 Day 8±1 d; Visit 4 Day 22±2 d; Visit 5 Day 29±3 d; Visit 6 Day 43±4 d; Visit 7 Day 50±4 d; Visit 8 Day 85±7 d; Visit 9 Day 184±9 d.
- i) Only for the first 6 subjects per group. Questioning on and documentation of AEs as well as systemic and local reactions, the latter in case of upcoming dose decision meetings.
- j) Only IMP-related AEs and any SAEs except proven COVID-19 cases which have to be reported regardless on severity and relatedness to the trial drug until the last scheduled FU Visit as described in Section 10.3.1.9.
- k) Blood draw for anti-SARS-CoV-2 antibodies.
- I) For Cohorts 1 and 8, immunization with at least 1 h intervals between subjects for the first 6 subjects and then with of at least 30 min intervals for the remaining 6 subjects. For all other cohorts and for all boost immunization, the intervals between subjects will be at least 30 min.
- m) Oral swipe for SARS-CoV-2 testing either on Day -1 or at the Visit 1 on Day 1.
- n) The timing of the listed "research" blood draw days may be adapted within the 200 mL maximum volume if justified by the collected data. Leftover blood after completion of the immunogenicity assessments may be used for additional analyses as described in Section 8.7 (Genetics) and/or Section 8.8 (Biomarkers).
- For subjects who have given consent, one aliquot of the blood sample drawn for analysis of CMI may be used for HLA typing to allow additional analysis of T-cell receptor repertoire and/or phenotypic characterization of T cells specific to vaccine-encoded antigens.
- p) If HLA typing using the blood sample collected with Lithium Heparin is not conclusive, EDTA-blood will be drawn for HLA testing.
- q) Only cohorts starting prime dosing after approval of protocol amendment 06.

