- f) Clinical laboratory tests: (Chemistry) alkaline phosphatase, creatinine, ferritin, C-reactive protein, albumin, alanine aminotransferase, amylase, aspartate aminotransferase, gamma glutamyl transpeptidase, total bilirubin, blood urea nitrogen, glucose, lipase, sodium, potassium, calcium; (Hematology) hemoglobin, hematocrit, red blood cell count, white blood cell count and differential (neutrophils, lymphocytes, monocytes, eosinophils, basophils), platelet count. Only in women who are not WOCBP (to confirm postmenopausal status): follicle stimulating hormone at Visit 0.
- g) Viral screening for human immunodeficiency virus (HIV) 1 or 2, hepatitis B, hepatitis C.
- h) Flexibility for visit days: Visit 3 Day 8±1 d; Visit 4 Day 22±2 d; Visit 5 Day 29±3 d; Visit 5a Day 36±3 d; Visit 6 Day 43±4 d; Visit 7 Day 50±4 d; Visit 8 Day 85±7 d; Visit 9 Day 184±9 d; Visit 10 Day 365±14 d; Visit 11 Day 547±14 d; Visit 12 Day 730±14 d.
- i) Only for HIV-positive subjects (done locally).
- j) Visits 8 and 9, only IMP-related AEs and any SAEs. Visits 10, 11, and 12, only any SAEs except proven COVID-19 cases which have to be reported regardless on severity and relatedness to the trial drug until the last scheduled FU Visit as described in Section 10.3.1.9. For subjects who receive non-trial SARS-CoV-2 vaccinations, the AEs expected to be captured after these vaccinations are within the frame of post-marketing safety data reporting (see Section 8.3.1).
- k) Blood draw for anti-SARS-CoV-2 antibodies.
- I) For first immunization in Cohort 13, immunization with at least 30 min intervals between the primary immunizations and 30 min between the boost immunizations. For Cohorts 11 and 12, the interval between the trial subjects will be at least 15 min for the prime immunizations and at least 5 min for the boost immunizations.
- m) Oral swipe for SARS-CoV-2 testing either on Day -1 or at the Visit 1 on Day 1.
- n) The timing of the listed "research" blood draw days may be adapted (within the 200 mL maximum volume) if justified by the collected data. Leftover blood after completion of the immunogenicity assessments may be used for additional analyses as described in Section 8.7 (Genetics) and/or Section 8.8 (Biomarkers). For subjects who receive non-trial SARS-CoV-2 vaccinations, there will be no blood sampling for immunogenicity or cell-mediated immune testing in the FU Visits.

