# 8.3.1 Time period and frequency for collecting AE and SAE information

For Cohorts 1 to 10, all AEs and SAEs will be collected from the date of subject consent until discharge from the trial only IMP-related AEs and any SAEs will be collected.

For Cohorts 11 to 13 and 14, all AEs and SAEs will be collected from the date of subject consent until Visit 7 (the EoT Visit). From Visit 7 through 9 only IMP-related AEs, SAEs, and SARS-CoV-2 infections will be collected. After Visit 9 (e.g., Visits 10, 11, and 12) until the last scheduled FU Visit (i.e., when the subject is discharged from the trial), any SARS-CoV-2 infections and SAEs will be collected.

For subjects in Cohorts 11 to 13 who receive a non-trial SARS-CoV-2 vaccination, AEs/SAEs will be collected as specified above until the date when the subject was vaccinated with the non-trial SARS-CoV-2 vaccine. The AEs expected to be captured after non-trial SARS-CoV-2 vaccination are within the frame of post-marketing safety data reporting.

All SAEs (initial and follow-up reports) will be recorded and reported to the sponsor or designee within 24 h after becoming aware of the event, as indicated in Section 10.3.1.10.

Investigators are not obligated to actively seek AEs or SAEs after conclusion of the trial participation. However, if the investigator learns of any SAE, including a death, at any time after a trial subject has been discharged from the trial, and he/she considers the event to be reasonably related to the IMP administration or trial participation, the investigator must promptly notify the sponsor.

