## 6. Statistical Analyses

## 6.1. General Considerations

The following described statistical analyses only refer to Part A of the study.

No formal statistical testing will be done.

Unless otherwise specified, analyses will be based on data pooled across all study sites.

Data assessed after the vaccination with a non-trial vaccine will be excluded from all statistical analyses.

Clarifications:

- Data assessed on the same day as the non-trial vaccination will remain in the analysis.
- If the date of non-trial vaccination is missing, but month and year information is available, data assessed after the last day of the respective month will be excluded from statistical analysis.

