## 6.1.1. Tables and Listings

#### Tables

In general, data will be summarized by groups (i.e., by vaccine type [BNT162a1, BNT162b1, BNT162b2, BNT162c2 SD and BNT162c2 P/B] and cohort) and all cohorts combined for each type (cohort-total). Furthermore, selected cohorts may be combined. The cohorts and cohort-total will be presented in columns and the different vaccine types in different tables.

There may be additional total columns for younger (18 to 55 years) and older (56 to 85 years) subjects.

Descriptive summary tables as well as figures will be based on scheduled visits.

Continuous variables will be summarized by group using the following descriptive statistics: number of subjects with non-missing data (n), mean, standard deviation (SD), median, minimum (min) and maximum (max).

Descriptive statistics of titer and fold increase of titer will additionally include geometric mean and its two-sided 95% confidence interval (CI). The geometric mean titer (GMT) is calculated as the mean of the logarithm of the functional antibody titers, back-transformed into the original scale. Two-sided CIs will be obtained by calculating CIs using t-distribution for the mean of the logarithmically transformed assay results and transforming the limits back to the original scale.

Geometric mean fold rise (GMFR) is calculated as the mean of the difference of logarithmically transformed assay results (post vaccination time point – pre vaccination time point) and back-transformed into the original scale. Two-sided CIs will be obtained by calculating CIs using Student's t-distribution for the mean difference of the logarithmically transformed assay results and transforming the limits back to the original scale.

Categorical variables will be summarized by group presenting absolute and relative frequencies (n and %) of subjects in each category (including the category 'missing' if applicable).

Percentages will be calculated based on the number of subjects in the respective analysis set (N) as denominator if not stated differently. Percentages may be presented with exact 95% Clopper-Pearson CIs.

SDs as well as CIs will only be calculated if values of at least 3 subjects are available.

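### In the BNT162b2 After Day 28 table, late SAE, death and COVID-19 percentages are not comparable between Cohorts 11–13 (680 d planned) and Cohorts 1–10 and 14 (134 d planned)

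*SAP*

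**What the plan says.** **The interval.** SAP 6.4.3 defines a late interval for all AEs, related or not. It begins "After day 28 after boost immunization", or after 28 days from the prime dose if no boost was given. No end day is stated.

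**The statistic.** Under the AEs heading of the same section, the "number and percentage of subjects reporting at least one AE and the number of AEs will be summarized for the above defined time interval". The rows include any SAE, related SAE, deaths and confirmed COVID-19. No denominator is given there, so the default in SAP 6.1.1 applies: "Percentages will be calculated based on the number of subjects in the respective analysis set (N) as denominator if not stated differently". For AEs that set is the Safety Set. Tables are made separately for each vaccine type, with one column per cohort and a cohort-total.

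**Follow-up.** Protocol 1.1 (Trial duration) plans "approximately 223 d for Cohorts 1 to 10 and 14, and 760 d for Cohorts 11 to 13". For Cohorts 11–13 after Visit 9, Protocol 8.3.1 says that "any SARS-CoV-2 infections and SAEs will be collected" until the last follow-up visit. COVID-19 cases and SAEs are likewise collected to the last visit in the other cohorts.

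**Individual stops.** Protocol 7.2 withdraws subjects in Cohorts 11–13 who receive a non-trial SARS-CoV-2 vaccine. SAP 6.1 adds, for every cohort: "Data assessed after the vaccination with a non-trial vaccine will be excluded from all statistical analyses". Nothing removes these subjects from N.

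**The concern.** A percentage of subjects with at least one event rises with the length of observation. In the BNT162b2 table, columns observed to Day 184 stand beside columns planned to Day 730, and the cohort-total pools both. If the underlying risk were the same everywhere, the table would still show more late SAEs, deaths and COVID-19 in the 3/30 µg, 30/30 µg and immunocompromised expansion cohorts than in the dose-ranging cohorts and Cohort 14. A reader could take that for a regimen or population signal.

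For unrelated late SAEs and for COVID-19, this is the only planned summary table; otherwise there are only listings. Elsewhere the SAP does fit the denominator to the data available: diary information in the interval for reactogenicity (6.4.1), and data at the visit for seroconversion (6.5.3). The longest and most uneven interval has no such provision.

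**Working it through.** **1. Reproduce the plan's own figures.** The boost is at "Visit 4 Day 22±2 d". The last visit of the P/B dose-ranging schedule is in "Visit 8 Day 85±7 d; Visit 9 Day 184±9 d", and Cohort 14 also ends at Day 184 (Protocol Table 9). Cohorts 11–13 end at Visit 12, Day 730 (Protocol Table 8).

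- 184 − 22 = 162 d and 730 − 22 = 708 d, which match the schedules' rows for days since the last dose.
- Total durations also reproduce: 184 + 30 + 9 = 223 and 730 + 30 = 760.

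**2. Planned time in the late interval** (days after the last dose, minus 28):

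- P/B Cohorts 1–10 and Cohort 14: 162 − 28 = **134 d**
- Cohorts 11–13: 708 − 28 = **680 d**
- Ratio: 680 / 134 = **5.07**
- BNT162c2 single dose: 183 − 28 = 155 d in every cohort
- No boost given: 183 − 28 = 155 d in P/B Cohorts 1–10 and 14, and 729 − 28 = 701 d in Cohorts 11–13

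The visit windows (±9 d and ±14 d) give 125–143 d and 666–694 d.

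**3. What the schedule alone does to the percentages.** The documents give no late event rate. I assume a constant rate, equal in all cohorts, and full planned follow-up: expected % = 1 − exp(−rate × days / 365.25).

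| Assumed rate per 100 person-years | 134 d | 680 d | Ratio |
|---|---|---|---|
| 2 | 0.7% | 3.7% | 5.0 |
| 3 | 1.1% | 5.4% | 5.0 |
| 5 | 1.8% | 8.9% | 4.9 |
| 10 | 3.6% | 17.0% | 4.7 |
| 20 | 7.1% | 31.1% | 4.4 |
| 40 | 13.6% | 52.5% | 3.9 |

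**4. The cohort-total.** Protocol Table 5 plans at most 290 BNT162b2 subjects: 10 × 12 + 20 = 140 in Cohorts 1–10 and 14, and 30 + 90 + 30 = 150 in Cohorts 11–13. Planned person-time is 140 × 134 = 18,760 d and 150 × 680 = 102,000 d. Cohorts 11–13 supply 102,000 / 120,760 = 84% of it with 52% of the subjects (150/290). At 10 per 100 person-years the total would read (140 × 3.6 + 150 × 17.0) / 290 = 10.5%, which describes neither group.

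**5. Effect of early stops.** The documents give no vaccination dates. Suppose every Cohort 11–13 subject stopped on the same day, and the other cohorts reached Day 184:

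| Stop day | Days in interval | Ratio to 134 d |
|---|---|---|
| 184 | 134 | 1.0 |
| 275 | 225 | 1.7 |
| 365 | 315 | 2.4 |
| 547 | 497 | 3.7 |
| 730 | 680 | 5.1 |

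**The case against.** The trial is descriptive. There is no hypothesis test, randomization or planned between-cohort comparison of late events. The primary AE endpoint uses windows of at most 28 d per dose and is untouched. Completion and discontinuation are tabulated by cohort, with individual dates listed (SAP 6.2), so a careful reader can see that follow-up was unequal. All of this stands, and it limits the weight of the point. It does not make the BNT162b2 columns comparable.

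Four stronger readings are tempting, and the documents do not support them.

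- *All the late tables are affected.* The 134 d against 680 d contrast exists only for BNT162b2. In the BNT162a1, BNT162b1 and BNT162c2 tables, planned time is the same in every column, apart from missed boosts and individual stops.
- *Cohorts 11, 12 and 13 cannot be compared with one another.* They share one schedule. Individual stops might differ between them, but nothing in the documents shows it.
- *Actual exposure differs five-fold.* That is the planned figure. Protocol 1.1 already says that approval of a third dose has affected the two-year follow-up, and Protocol 4.4 allows an early end. The SAP exclusion can also shorten the 134 d.
- *This is the only tabulation of late SAEs.* Related events through Visit 10 (Day 365) also enter the TEAE tables.

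A rate per person-year will not remove every difference. COVID-19 risk varies with calendar time, and Cohort 13 is immunocompromised by design. The rate removes the part due to unequal observation time, and no more.

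**Conclusion.** The point holds for one table. In the BNT162b2 After Day 28 summary, the SAE, related SAE, death and COVID-19 percentages are not comparable between Cohorts 11–13 and Cohorts 1–10 and 14. The cohort-total pools planned follow-up that differs by up to 5.1-fold.

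Under equal assumed rates of 2 to 40 per 100 person-years and full planned follow-up, the schedule alone multiplies the percentage by about 3.9 to 5.0. Earlier stops in Cohorts 11–13 would bring this down towards 1. The planned day counts come from the visit schedules; the event rates and stop days are assumptions.

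A reader might infer that the percentages mainly reflect observation time. That is not shown: the documents give no event rates and no vaccination dates, and population and calendar time also matter. The point is a worthwhile correction to a descriptive safety table, and it does not challenge the primary analysis.

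**What to change.** In SAP 6.4.3, keep n (%). For the SAE, related SAE, death and COVID-19 rows of the BNT162b2 table, add:

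1. **Common horizon.** The proportion with an event from day 29 after the last dose up to Day 184, in all cohorts. Day 184 is a planned visit in every BNT162b2 cohort.
2. **Person-time rate.** Total person-time from day 29 after the last dose to the earliest of last contact, end of trial, or the date from which SAP 6.1 excludes data. Report subjects with a first event per 100 person-years, with time counted to the first event, and an exact Poisson CI.

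The cut-off in (2) should be any non-trial vaccination, with the same-day and partial-date rules of SAP 6.1. If it were limited to SARS-CoV-2 vaccines, person-time would go on accruing after another vaccine while the events were dropped, and the rate would be too low.

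**Cost.** One derived variable and extra columns, with no new data. The vaccination dates are already needed for SAP 6.1, and the discontinuation dates for SAP 6.2.

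**Downside.** A 12-subject cohort contributes at most about 12 × 134 / 365.25 = 4.4 person-years if all are boosted. With no events, the upper 95% limit is 3.69 / 4.4, or about 84 per 100 person-years. The rate is therefore mainly useful for Cohorts 11–13 and the pooled columns. In the small cohorts the Day 184 proportion does most of the work.
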